#### **Number of patients:**

A maximum of 36 patients (up to 12 patients in phase I and up to 24 patients in the phase II) will be enrolled in the study.

#### **Phase I study**

Nine to 12 patients will be treated. Open study to phase II if first cycle RUXOLITINIB attributable toxicity in  $\leq 2$  of 6. If first cycle RUXOLITINIB-related DLTs are observed in more than 2/6 patients, this dose level would exceed the MTD, and 3 patients will be treated at the next lower dose level according to Table 1.

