**3.0 STUDY DESIGN****3.1 Design**

In this non-randomized Phase I/II investigator-initiated, single center trial, cohorts of patients will be treated with increasing doses of ruxolitinib in combination with a decitabine at a dose of 20mg/m^2 daily intravenously over 5 days. We will use an initial dose of ruxolitinib of 10 mg orally twice daily. Patients will receive ruxolitinib for the first 28 days in addition to decitabine on days 1-5 of each cycle. Cycles will be repeated every 4-6 weeks depending on tolerance and the recovery of the counts. Patients who become eligible for allogenic stem cell transplant may leave the study at any time after the first cycle.

After the first cycle of therapy, modifications to the dose of Ruxolitinib felt to be in the best interest of the patient are allowed after discussion with the Principal Investigator of the study and with the documentation of the discussion in the patient's medical records.

For the purposes of assessing safety, DLTs will be defined as those adverse events occurring in the first cycle (i.e. 28 days) of therapy that are not clearly related to disease, intercurrent illness or concurrent medication. These events will be defined based on the NCI CTCAE version 4 as follows:

- Any Grade 3 or higher non-hematologic toxicity (with the exceptions of Grade 3 or higher nausea, vomiting, or diarrhea, which will be considered DLTs only after optimal prophylactic measures have been prescribed; Grade 3 elevations of AST/ALT must be sustained for more than 4 days or reach Grade 4 to be considered a DLT. Grade 3 elevations in bilirubin must occur in the setting of a direct bilirubin >1 to be considered a DLT. Fatigue must be Grade 4 to be considered a DLT)
- Any Grade 4 hematologic toxicity lasting at least 42 days from the first day of the last cycle of therapy with a bone marrow cellularity of ≤5% and no evidence of leukemia. No dose modification will occur until any potential DLTs is fully assessed

MTD is defined as the highest dose studied for which the incidence of DLT is less than or equal to 17% (1 out of 6).

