#### **8.2 Dose escalation scheme for phase I**

Cohorts of 3-6 patients each will be treated with increasing doses of ruxolitinib in a progression of 10mg, 15mg, 25 mg and 50 mg twice daily.

At least 3 patients will be treated at each dose level. All patients treated at the preceding dose level will be observed a minimum of 5 weeks before dose escalation occurs. Dose escalation will proceed as follows:

- If none of the initial 3 evaluable patients in a cohort experiences first cycle dose limiting toxicity (DLT), then a new cohort of 3 patients will be treated at the next higher dose level.
- If one of 3 evaluable patients in a cohort experiences DLT, then up to an additional 3 patients will be treated at the same dose level. Escalation will continue if only one of the 6 patients experiences a DLT.
- In the event that 2 of 3 evaluable patients, or 2 of 6 patients in the first cohort experiences a DLT, then the next cohort of patients will be treated at a lower dose level (dose level -1) and no further dose escalation will occur in this step. Three patients will be enrolled at this dose level, if 0 or 1 patients experiences a DLT, a further 3 patients will be enrolled at this dose level. If overall 0 or 1 patient experiences a DLT at this dose level, this dose will be established as the maximum tolerated dose (MTD).
- If two or more evaluable patients in the cohort experience DLT, then the maximum tolerated dose (MTD) will have been exceeded, and no further dose escalation will occur. The previous dose will be considered as the MTD.
- If only three patients were treated at the dose level under consideration as the MTD, then up to an additional 3 patients will be accrued. If no more than one patient at that dose level experiences DLT, then that dose level will be confirmed as the MTD. If two or more patients in that cohort experience DLT, then the previous dose level will be studied in the same fashion.

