#### **Dose Escalation Procedures:**

The dose of treatment agent will be escalated in successive cohorts of patients. The starting dose is at dose 0 as shown in table 1. Enroll 3 patients at the dose level and proceed to the next higher dose level with a cohort of 3 patients until at least 1 patient experiences a dose-limiting toxicity (DLT). If only 1 of 3 patients experiences a DLT at a given dose level, enter 3 additional patients at the current dose level. If only 1 of 6 patients experiences a DLT at a given dose level, proceed to the next higher dose level with a cohort of 3 patients. If at least 2 of 3 or 2 of up to 6 patients experience a DLT at a given dose level, then the MTD has been exceeded (stopping dose). Once the MTD has been exceeded, treat another 3 patients at the MTD if there were only 3 patients treated at that dose level. The MTD is defined as the highest dose level in which 6 patients were treated with at most 1 experiencing a DLT during the 1st cycle. One cycle of therapy is defined 5 days of decitabine and 28 days of RUXOLITINIB but treatment with RUXOLITINIB can be continued until the next cycle (start of decitabine) in the absence of toxicity, beyond the day 28 and without interruption.

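### Section 8.1 opens phase II at 2 of 6 patients with toxicity, while sections 3.1, 8.2, 8.3 and 13.0 limit the MTD to 1 of 6 with a DLT

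*Combined protocol and SAP*

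**What the plan says.** Section 8.1, under the subheading on the phase I study, gives two linked rules. The first reads "Open study to phase II if first cycle RUXOLITINIB attributable toxicity in" at most 2 of 6. The second reads "If first cycle RUXOLITINIB-related DLTs are observed in more than 2/6 patients, this dose level would exceed the MTD", and then sends three patients to the next lower level.

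The other statements of the limit differ:

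- Section 3.1 defines the MTD by a DLT incidence of 17% or less, glossed as 1 of 6. Section 8.3 says below 17%, with the same gloss.
- Section 8.2 continues escalation when only one of six has a DLT, and says: "If two or more evaluable patients in the cohort experience DLT, then the maximum tolerated dose (MTD) will have been exceeded".
- Section 13.0, on dose escalation, rejects a level with two DLTs among three patients and gives the same limit for an expanded cohort: "2 of up to 6 patients experience a DLT at a given dose level, then the MTD has been exceeded". It adds: "The MTD is defined as the highest dose level in which 6 patients were treated with at most 1 experiencing a DLT".
- Section 8.1 itself, below Table 1, also puts a level above the MTD at 2 or more of 6. It counts a different event there: grade 3-4 non-haematological toxicity related to ruxolitinib.

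The phase II paragraph of section 13.0 takes its dose from the phase I recommendation and excludes from phase II the phase I patients treated at the MTD.

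**The concern.** Two DLTs in six patients is the borderline result of a 3+3 design, and it is a likely one. At that result the section 8.1 paragraph says that the MTD is not exceeded and that phase II may open. Sections 8.2 and 13.0 say that the MTD is exceeded and that the dose must come down. Both cannot be followed. Someone who turns to the treatment section to decide whether to open phase II finds the permissive rule.

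Phase I fixes the ruxolitinib dose for up to 24 phase II patients. Following section 8.1 could expose them to a dose that the statistical section rejects. It could also cost the efficacy assessment, because phase II may then stop early for toxicity.

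**Working it through.** **1. The stated limit.** 1/6 = 16.7%, which meets both the section 3.1 wording (17% or less) and the section 8.3 wording (below 17%). 2/6 = 33.3% meets neither and is twice the observed rate at the limit. The difference in wording between 3.1 and 8.3 therefore does not matter for six patients.

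**2. The rules side by side, with both DLTs ruxolitinib-related.**

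| DLTs in 6 | Section 8.1, phase I study | Sections 8.2 and 13.0 |
|---|---|---|
| 0 or 1 | phase II may open | within the MTD |
| 2 | phase II may open; MTD not exceeded | MTD exceeded |
| 3 or more | MTD exceeded | MTD exceeded |

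Only the middle row conflicts.

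**3. How often the middle row decides.** The documents give no phase I DLT rates, so the true rate p is assumed. Take one dose level that stops if 2 or more of the first 3 have a DLT and is otherwise expanded to 6. Let f(k) be the binomial probability of k DLTs in 3 patients.

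- P(at most 1 of 6) = f(0)² + 2·f(0)·f(1)
- P(exactly 2 of 6, not stopped) = f(0)·f(2) + f(1)²

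Worked at p = 0.20: f(0) = 0.512, f(1) = 0.384, f(2) = 0.096.

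- At most 1: 0.2621 + 0.3932 = 0.655
- Exactly 2: 0.0492 + 0.1475 = 0.197
- Sum: 0.852

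| Assumed p | At most 1 of 6 | Exactly 2 of 6 | At most 2 of 6 |
|---|---|---|---|
| 20% | 0.655 | 0.197 | 0.852 |
| 33% | 0.358 | 0.263 | 0.621 |
| 40% | 0.233 | 0.249 | 0.482 |

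The section 8.1 paragraph states no stop at 2 of 3. Without one, P(at most 2 of 6) is the plain binomial sum (1−p)⁶ + 6p(1−p)⁵ + 15p²(1−p)⁴, which is 0.901, 0.687 and 0.544 at the three rates. The gap is then wider.

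**4. What the phase II toxicity rule would catch.** Table 7 was applied alone, with looks at 4, 6, …, 22 patients and stopping counts 2, 3, 3, 4, 4, 5, 5, 6, 6, 7. At a 30% toxicity rate it stops with probability 0.732. Table 9 gives 0.7381 at 30% toxicity and 40% response; that figure also includes futility stops, so the two agree well. At 33% the rule stops 0.811 of trials after an average of 10.9 patients. At 40% it stops 0.931 after an average of 8.2.

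**The case against.** The strongest reply is that the intended rule is plain. Sections 3.1, 8.2, 8.3 and 13.0 agree on 1 of 6, section 8.1 uses the same cut below Table 1, and section 13.0 announces that its next section holds the detailed escalation rules. The section 8.1 paragraph is the outlier. That stands, and it settles which text to correct. It does not remove the conflict, because no clause ranks one rule above another.

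A reader might infer that section 8.1 holds the only numeric condition for opening phase II. The documents do not support that. By excluding phase I patients treated at the MTD from phase II, section 13.0 implies that the phase II dose is the MTD, which it defines numerically.

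A reader might also infer that a dose with 2 of 6 DLTs would reach phase II unchecked. That too goes beyond the text. Section 8.1 requires a cohort summary to the IND Medical Monitor before dose levels are advanced or changed, and Table 7 monitors toxicity in phase II. Both safeguards are partial. The text does not say that the summary covers the opening of phase II. Table 7 acts only after phase II patients are exposed, and its endpoint (non-haematological grade 3 or higher, haematological grade 4 or higher) is not the section 8.3 DLT.

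Last, the event counts differ. The section 8.1 paragraph counts toxicity or DLTs tied to ruxolitinib, while section 8.3 counts events not clearly due to disease, intercurrent illness or concurrent medication. The claim is therefore limited to the case where both DLTs are ruxolitinib-related.

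**Conclusion.** This is an internal inconsistency in a dose-safety rule, and the section 8.1 paragraph is wrong as written. It is not a criticism of the 3+3 design. With exactly 2 of 6 patients having ruxolitinib-related DLTs, section 8.1 lets the dose into phase II and sections 8.2 and 13.0 reject it.

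For a single dose level, the looser cut raises the chance of going forward by about 20 percentage points at an assumed true rate of 20%, 26 at 33% and 25 at 40%. These figures assume independent patients, expansion to six, a stop at 2 of the first 3, and the same event counted under both rules. They illustrate one dose level. They do not predict which dose this trial would select, because that also depends on the unknown rates at all four levels and on how the two sets of rules would be combined.

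**What to change.** Replace the threshold sentences in section 8.1, under the phase I study subheading, with:

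> Phase II opens only at a dose level at which 6 patients were treated and at most 1 had a first-cycle DLT (section 8.3). If 2 or more of up to 6 patients have a DLT, that level exceeds the MTD, and the next lower level is expanded to 6 patients if only 3 were treated there.

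The last clause matches section 13.0, which says to "treat another 3 patients at the MTD if there were only 3 patients treated at that dose level". The change is one paragraph, with no new procedures. The price is that a dose with an assumed true DLT rate of 20% goes forward 66% rather than 85% of the time, which sections 8.2 and 13.0 already accept.

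A separate matter, not part of this fix, is the size of phase I. The same paragraph says "Nine to 12 patients will be treated", and section 6.0 and the patient-number paragraph of section 8.1 also cap phase I at 12. Section 13.0 allows 18 evaluable patients, and section 6.0 allows up to 6 replacements. Testing all four levels with six patients at the MTD needs at least 3 + 3 + 3 + 6 = 15 evaluable patients. Which cap is right is for the sponsor to decide.

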**Table 1 – RUXOLITINIB dose**

Dose level	RUXOLITINIB (mg PO) (x 28 days)	No of evaluable patients
0	10 BID	3
1	15 BID	3
2	25 BID	3
3	50 BID	3

We will utilize the above design format to determine the tolerable dose of RUXOLITINIB to be used in combination with decitabine, with 25 mg PO BID as the target dose. The enrollment of participants will be staggered; all the participants in each cohort will finish the first cycle of therapy followed by 7 days of observation (i.e. day 35 of therapy) before proceeding to the next cohort. Subsequence cycles will begin on the first day of decitabine therapy and, in the absence of toxicity, RUXOLITINIB administration will not be interrupted. Patients who come off the study during the first cycle for reasons other than development of dose limiting toxicity (e.g. disease progression) will be replaced in order to ensure adequate chance for the assessment of DLT.

If grade 3-4 non-hematological RUXOLITINIB-related toxicities are observed in ≥ 2/6 patients, this dose level would exceed the MTD.

If grade 3-4 RUXOLITINIB-related toxicities are observed in 0-1/6 patients, the study will continue at the RUXOLITINIB dose of 15, 25, and 50 mg P.O. BID x 28 days plus chemotherapy, as outlined above. We will examine the dose of 50 mg BID to assess its tolerability and if well tolerated, this will be the dose to move to phase II. However, the target dose for phase II is 25 mg po BID x 28 days.

Cycles will be repeated approximately every 4 to 6 weeks, depending on the recovery of the blood counts and will continue until clinically significant progression, withdrawal of consent or unacceptable toxicity for a maximum of 24 cycles (see section 13.0).

Toxicities to be monitored include any grade 3 or 4 non-hematological toxicity felt to be related to RUXOLITINIB and prolonged cytopenias (lasting for more than 42 days after the initiation of the treatment) felt to be related to the treatment and not the underlying disease. Patients with prolonged cytopenias should have a bone marrow exam around day 42 to establish whether this is due to the treatment or whether there is persistent disease. In the case of the former, treatment should be discontinued.

Prior to advancing/changing dose levels, a cohort summary must be completed and submitted to the IND Medical Monitor for review.

Each cohort will have up to 6 patients enrolled.

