### **8.3 Definition of DLT and MTD:**

For the purposes of assessing safety, DLTs will be defined as those adverse events occurring in the first cycle (i.e. 28 days) of therapy that are not clearly related to disease, intercurrent illness or concurrent medication. These events will be defined based on the NCI CTCAE version 4 as follows:

- Any Grade 3 or higher non-hematologic toxicity (with the exceptions of Grade 3 or higher nausea, vomiting, or diarrhea, which will be considered DLTs only after optimal prophylactic measures have been prescribed; Grade 3 elevations of AST/ALT must be sustained for more than 4 days or reach Grade 4 to be considered a DLT. Grade 3 elevations in bilirubin must occur in the setting of a direct bilirubin  $>1$  to be considered a DLT. Fatigue must be Grade 4 to be considered a DLT)
- Any Grade 4 hematologic toxicity lasting at least 42 days from the first day of the last cycle of therapy with a bone marrow cellularity of  $\leq 5\%$  and no evidence of leukemia. No dose modification will occur until any potential DLTs is fully assessed

MTD is defined as the highest dose studied for which the incidence of DLT is less than 17% (1 out of 6).

**Table 2 - Criteria for dose modifications of RUXOLITINIB due to study drug-related toxicity – These must be clearly related to ruxolitinib and not the underlying disease; to be determined by PI and treating physician**

Worst Toxicity CTCAE Grade* unless otherwise specified (Value)	Dose Modification Guidelines At any time during a cycle of therapy (including intended day of dosing)	
HEMATOLOGICAL TOXICITIES		
Thrombocytopenia	< 20 x 10  /L	Interrupt study treatment dosing until resolved to ≥ 20 x 10  /L, then restart study treatment at reduced level as per Table 5
	> 20 x 10  /L + grade 3 bleed	Interrupt study treatment dosing until bleeding is resolved and platelet count is at level before bleed was noted, then resume study treatment at reduced level as per Table 5
Neutropenia (ANC)	Grade 4 (ANC < 0.5 x 10  /L)	Interrupt study treatment dosing until resolved to ≤ grade 2, or baseline, then: 
 
• If resolved within 7 days restart study treatment at an unchanged dose level
 
• If resolved in more than 7 days then restart study treatment at reduced level as per Table 5
 

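### The Phase I study paragraph of Section 8.1 accepts 2 of 6 toxicities for opening phase II, while every other phase I rule treats 2 of 6 as exceeding the MTD

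*Combined protocol and SAP*

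**What the plan says.** **Where 2 of 6 is accepted.** The Phase I study paragraph in Section 8.1 begins "Open study to phase II if first cycle RUXOLITINIB attributable toxicity in" at most 2 of 6. It continues: "If first cycle RUXOLITINIB-related DLTs are observed in more than 2/6 patients, this dose level would exceed the MTD". Three patients then go one level down in Table 1.

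**Where 2 of 6 is rejected.**
- Section 8.1, text after Table 1: toxicity at or above "2/6 patients, this dose level would exceed the MTD".
- Section 8.2: two or more DLTs in a cohort exceed the MTD, and escalation continues only at one in six.
- Section 13, Dose Escalation Procedures: at 2 of 3 or 2 of up to 6, "then the MTD has been exceeded (stopping dose". Also: "The MTD is defined as the highest dose level in which 6 patients were treated with at most 1 experiencing a DLT".
- Section 3.1: "the incidence of DLT is less than or equal to 17% (1 out of 6".
- Section 8.3: "the incidence of DLT is less than 17% (1 out of 6".

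**Below the starting dose.** If the first cohort has 2 of 3 or 2 of 6 DLTs, Section 8.2 says "then the next cohort of patients will be treated at a lower dose level (dose level -1". Tables 1 and 5 list levels 0 to 3 only (10, 15, 25 and 50 mg BID), and Section 13 starts at level 0.

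**The concern.** The threshold decides which dose goes into phase II. At exactly 2 of 6 the plan gives two opposite instructions, and no section says which prevails. The looser one is in the paragraph that says when to open phase II, so it could be followed in good faith. The conflict can arise at any dose level, including the 25 mg BID target.

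The second gap has the same source: phase I decision rules written in several places and not reconciled. If 10 mg BID proves too toxic, Section 8.2 calls for another cohort, and allows its dose to become the MTD, without giving a dose.

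**Working it through.** **The plan's own figure.** 1/6 = 16.7%, which rounds to the stated 17%. It satisfies both versions of the cap (at most 17% in Section 3.1, below 17% in Section 8.3), so that difference does not matter here. 2/6 = 33.3%, twice the cap.

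**Inputs.** The documents give no DLT rate for the combination, so the true rate p is assumed; q = 1 − p. The level enters a first cohort of 3. With 1 DLT it expands by 3. With 0 DLTs it receives 3 more when it is confirmed as the MTD (Sections 8.2 and 13). Full expansions of 3 are assumed.

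**Formulas.**
- Exactly 2 of 6: 1/3 then 1/3, (3pq²)², plus 0/3 then 2/3, q³ × 3p²q. The sum is 12p²q⁴.
- Accepted at no more than 1 of 6: q⁶ + 6pq⁵.
- Accepted at no more than 2 of 6, keeping Section 8.2's stop at 2 of the first 3: the sum of the two lines above.
- Plain six-patient reading of the Phase I study paragraph: P(X ≤ 2), X binomial(6, p).

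At p = 0.30: (3 × 0.3 × 0.49)² + 0.343 × 3 × 0.09 × 0.7 = 0.1945 + 0.0648 = 0.2593. Accepted at no more than 1 of 6: 0.1176 + 0.3025 = 0.4202. Sum: 0.6795.

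| True DLT rate (assumed) | Exactly 2 of 6 | Accepted, ≤1 of 6 | Accepted, ≤2 of 6 with stop at 2 of 3 | Accepted, plain ≤2 of 6 |
|---|---|---|---|---|
| 10% | 7.9% | 88.6% | 96.4% | 98.4% |
| 20% | 19.7% | 65.5% | 85.2% | 90.1% |
| 30% | 25.9% | 42.0% | 67.9% | 74.4% |
| 40% | 24.9% | 23.3% | 48.2% | 54.4% |

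**What phase II would then do.** I applied the Table 7 toxicity boundaries alone (stop at 2 or more of 4, 3 of 6 or 8, 4 of 10 or 12, 5 of 14 or 16, 6 of 18 or 20, 7 of 22), looking every 2 patients from 4.
- 30% toxicity: stopped with probability 0.73, mean about 12 patients.
- 33%: 0.82, about 11.
- 40%: 0.93, about 8.

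Table 9 agrees. In its rows with 40% response, where futility rarely stops the trial, it gives 0.7381 and 12 patients at 30% toxicity, and 0.9328 and 8 patients at 40%.

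**Below level 0.** The chance that level 0 fails in escalation is 1 − [q³ + 3pq² × q³]: 2.7, 9.4, 29.1 and 50.6% at p = 5, 10, 20 and 30%. There are three textual routes to the missing dose:
- the first-cohort bullet of Section 8.2;
- the last bullet of Section 8.2, if level 0 starts with 0 of 3, level 1 fails, and level 0's confirmation has 2 or more DLTs. This adds at most q³(3p²q + p³) = 0.6, 2.0, 5.3 and 7.4%;
- the step down in Table 1 in the Phase I study paragraph of Section 8.1.

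**The case against.** **Different events might be counted.** The text after Table 1 counts grade 3-4 ruxolitinib-related non-hematological toxicity, the Phase I study paragraph opens with attributable toxicity, and Sections 8.2 and 13 count DLTs. This does not reconcile them: the second sentence of the Phase I study paragraph counts first-cycle ruxolitinib-related DLTs and draws the same conclusion about the MTD at a different number.

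**The paragraph is an outlier.** Sections 3.1, 8.2, 8.3 and 13 and the text after Table 1 all set the limit at 1 of 6, and Section 13 presents its rules as the detailed ones. That stands. It makes this an internal inconsistency; a reader might infer a deliberate wish to accept a 33% DLT rate, and the documents do not support that.

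**Safeguards exist.** A reader might also infer that 24 patients would be treated at a dose that is too toxic. The phase II toxicity rule argues against that. As Section 13 words it, it counts non-hematological grade 3 or higher and hematological grade 4 or higher, without the 42-day requirement in Section 8.3, so it is at least as sensitive as the DLT definition. Medical Monitor review before a change of dose level helps too. None of these sets the phase I threshold.

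**The gap below level 0 harms nobody directly.** This largely stands. A cohort cannot be treated until a dose is set, and Section 13 already calls a failed level a stopping dose and sends nobody lower. Section 2.0 reports single-agent 25 mg BID as very well tolerated, so failure at 10 mg BID may be unlikely, although that experience is not with the combination. The reductions under Dose modifications in Section 8.1 are for individual patients and do not define a cohort dose.

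**Conclusion.** The conflict at exactly 2 of 6 is real and should be corrected. It falls on a fairly likely outcome: about 20 to 26% of levels with a true DLT rate of 20 to 40%. Over that range the looser limit adds those same 20 to 26 percentage points to the chance of acceptance, and at 40% it roughly doubles that chance (23.3 to 48.2%). The figures rest on assumed DLT rates and on keeping the stop at 2 of the first 3; a plain six-patient reading gives larger differences.

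The consequence is that phase II could open at a dose that the rest of the plan calls too toxic. Table 7 would usually limit exposure to about 8 to 12 patients on average at 30 to 40% toxicity, with 24 as the ceiling.

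The undefined level below 0 is a minor second point. It leaves an instruction that cannot be carried out; it does not expose patients to an excessive dose.

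**What to change.** 1. Reword the Phase I study paragraph of Section 8.1 so that phase II opens only at a dose level with at most 1 DLT in 6 patients, and 2 or more DLTs exceed the MTD. Count DLTs as defined in Section 8.3 both there and in the text after Table 1.
2. In Section 8.1 (Phase I study paragraph), Section 8.2 (first-cohort and last bullets) and Section 13, state that if level 0 has 2 or more DLTs, phase I stops with no MTD established. Delete the reference to level -1.

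The cost is wording in three sections. Neither change adds patients beyond what the text after Table 1, Section 8.2 and Section 13 already require. The price of the first is that some levels that would have gone forward at 2 of 6 will not, which is what the plan's own MTD definition intends.

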## 13.0 STATISTICAL DESIGN

### **Basis for sample size:**

#### **Phase I**

First, a phase I study is performed to assess the safety of different dosing regimens for RUXOLITINIB combined with decitabine. Four combination dose levels are defined (table 1). A 3+3 design will be used to for dose escalation. Detailed dose escalation rules are described in the following section. A maximum of 18 evaluable patients will enroll in the phase I study.

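### One paragraph of Section 8.1 opens phase II at a dose level with 2 of 6 DLTs, which Sections 3.1, 8.1 (under Table 1), 8.2, 8.3 and 13 place above the MTD

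*Combined protocol and SAP*

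**What the plan says.** Section 8.1, Phase I study, gives the trigger for phase II, "Open study to phase II if first cycle RUXOLITINIB attributable toxicity in", with a limit of 2 or fewer of 6. It repeats that limit from the other side: "If first cycle RUXOLITINIB-related DLTs are observed in more than 2/6 patients, this dose level would exceed the MTD". Both sentences therefore accept exactly 2 of 6.

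Every other statement of the rule rejects it:

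- Section 8.1, under Table 1: "RUXOLITINIB-related toxicities are observed in ≥ 2/6 patients, this dose level would exceed the MTD".
- Section 8.2: "If two or more evaluable patients in the cohort experience DLT, then the maximum tolerated dose (MTD) will have been exceeded". The previous dose is then taken as the MTD.
- Section 13, Dose Escalation Procedures: "2 of up to 6 patients experience a DLT at a given dose level, then the MTD has been exceeded". The MTD is the highest level with six treated and no more than one first-cycle DLT.
- Sections 3.1 and 8.3: DLT incidence at the MTD is at or below 17% (3.1) or below 17% (8.3). Each glosses the figure as 1 out of 6.

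Section 13, Phase I, says "Detailed dose escalation rules are described in the following section", which points to the stricter rule but does not say that it overrides Section 8.1. The phase I maximum is 12 in Section 6 and in two paragraphs of Section 8.1, but 18 evaluable in Section 13.

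**The concern.** The same data, 2 of 6 ruxolitinib-related DLTs at one level, lead to opposite decisions. The Phase I study paragraph opens phase II there, while the other sections step down. It is also the only place that states an explicit trigger for opening phase II, and it sits in the treatment section that site staff use.

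Phase I sets the starting dose for up to 24 phase II patients. If 25 mg BID, the target dose, shows 2 of 6, one rule starts those patients at 25 mg BID. The other rules give 15 mg BID, provided six patients at 15 mg show at most one DLT.

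**Working it through.** **The plan's own figure.** 1/6 = 16.7%, which matches the stated 17%. 2/6 = 33.3%, twice that limit. The difference between Section 3.1 (at or below 17%) and Section 8.3 (below 17%) does not matter: 16.7% passes both and 33.3% fails both.

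**One dose level.** Assume a true DLT rate p and 3+3 staging, with the level failing if 2 or 3 of the first 3 have a DLT. Write P0 = (1−p)³, P1 = 3p(1−p)² and P2 = 3p²(1−p).

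- P(at most 1 of 6) = P0² + 2·P0·P1
- P(exactly 2 of 6) = P1² + P0·P2

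| p | P0, P1, P2 | at most 1 of 6 | exactly 2 of 6 | at most 2 of 6 |
|---|---|---|---|---|
| 0.20 | 0.512, 0.384, 0.096 | 0.655 | 0.197 | 0.852 |
| 0.30 | 0.343, 0.441, 0.189 | 0.420 | 0.259 | 0.679 |
| 0.40 | 0.216, 0.432, 0.288 | 0.233 | 0.249 | 0.482 |

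With six patients always treated and no stop after the first three, the last column would be 0.901, 0.744 and 0.544.

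**Patients needed.**

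- Six at 25 mg BID: 3+3+6 = 12.
- Confirming 15 mg after that: 3+6+6 = 15.
- Six at 50 mg: 3+3+3+6 = 15.
- Confirming 25 mg after that: 3+3+6+6 = 18.

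**Whole trial.** I enumerated the four-level escalation exactly along the Section 13 path. I compared its MTD with the highest level that has six treated and at most 2 DLTs. The plan gives no DLT rates, so five curves are assumed for 10, 15, 25 and 50 mg BID: (2, 4, 8, 12%), (5, 8, 12, 20%), (5, 10, 20, 30%), (5, 10, 20, 40%) and (10, 15, 25, 40%).

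In the order of the curves, the Section 13 rule finishes within 12 patients with probability 0.039, 0.119, 0.197, 0.197 and 0.351. It finishes within 18 with probability 0.960, 0.904, 0.892, 0.889 and 0.890. The two thresholds give different doses, in trials finished within 18, with probability 0.136, 0.243, 0.323, 0.324 and 0.366 of all trials.

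Four curves have a level above 1/6. The chance of selecting such a level, at most 1 of 6 against at most 2 of 6:

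| Curve (%) | Share of all trials, finished within 18 | Rise (points) | Among trials finished within 18 | Rise (points) |
|---|---|---|---|---|
| 5, 8, 12, 20 | 0.482 → 0.593 | 11.1 | 0.534 → 0.656 | 12.3 |
| 5, 10, 20, 30 | 0.508 → 0.646 | 13.8 | 0.570 → 0.725 | 15.5 |
| 5, 10, 20, 40 | 0.500 → 0.643 | 14.3 | 0.562 → 0.723 | 16.1 |
| 10, 15, 25, 40 | 0.319 → 0.462 | 14.3 | 0.358 → 0.519 | 16.1 |

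The right-hand pair is the middle pair divided by the probability of finishing within 18, for example 0.482/0.904 = 0.534.

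**Within 12 patients.** Neither threshold selects a level above 1/6 in a trial completed by patient 12. Such trials end at 15 mg or lower, where every assumed rate is at most 15%. The conflict at 25 mg then arises only if phase II opens directly after 2 of 6 there. A 2-of-6 result at 25 mg is reached by patient 12 with probability 0.034, 0.052, 0.092, 0.092 and 0.080. For the third curve this is 0.95³ × 0.90³ × 0.384² = 0.092.

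**The case against.** The strongest reply is that Section 13 governs. It is the statistical design, it holds the detailed rule, and Sections 3.1, 8.2, 8.3 and the text under Table 1 agree with it. That makes the intended rule easy to infer, but nothing gives it precedence over an explicit trigger in the treatment section. Nor is the trigger one mistyped symbol, since the paragraph states the same threshold twice.

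A second reply is that the paragraph counts only ruxolitinib-attributable events. The text under Table 1 also counts ruxolitinib-related toxicity and sets the opposite limit. Two ruxolitinib-related DLTs also count as DLTs under Sections 3.1 and 8.3.

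Third, there are safeguards. A cohort summary goes to the IND Medical Monitor before dose levels change. Phase II accrual stops at 2 toxicities in 4 patients or 3 in 6, and Table 9 gives overall stopping probabilities of 0.74 to 0.93 at 30% toxicity. Section 8.1 also permits reduction to 15 or 10 mg BID. These limit the harm. But the medical monitor would be reading the same conflicting rules, and the stopping rule and dose reductions act only after patients have started at that dose.

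A reader might infer more than the documents support. With no limit on phase I size, the chance of opening phase II above 1/6 rises by 16 to 17 points (for example 60% to 75% on the third curve), but the plan caps phase I at 12 or 18, so those figures describe a trial that it does not allow. Nor does it follow that phase II will start too high: that needs exactly 2 of 6 at a level and staff who follow this paragraph.

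**Conclusion.** Wrong as written: an internal inconsistency in a dose-selection rule. The contradiction needs no assumption about toxicity, since 2 of 6 is accepted in one paragraph and rejected in five other places.

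Its size does rest on assumptions. Per level, accepting 2 of 6 adds about 20 to 26 percentage points to the chance of qualifying at true DLT rates of 20% to 40%. On the four relevant curves, the chance of selecting a level above 1/6 rises by 12 to 16 points among trials finishing within 18 patients, or 11 to 14 points as a share of all trials. The comparison follows the Section 13 path and changes only the final threshold. The Phase I study paragraph taken alone would not treat 2 of 6 as exceeding the MTD, so these figures do not describe a trial run entirely on it.

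**What to change.** Replace the two rule sentences in Section 8.1, Phase I study, with:

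> Phase II opens at the MTD of Section 13, the highest level with 6 patients treated and at most 1 first-cycle DLT. If 2 or more of the first 3, or 2 or more of up to 6, have a DLT, the level exceeds the MTD and the next lower level is taken to 6 patients; if this occurs at 10 mg BID, phase II does not open unless a lower level is defined.

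The last clause is needed because Table 1 has no level below 10 mg BID, and the dose level −1 of Section 8.2 is undefined.

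In the same change, use one phase I maximum. The 18 evaluable of Section 13 should replace 12 in Section 6 and in Section 8.1 (Number of patients, and Phase I study). The overall maximum becomes 18 + 24 = 42 instead of 36, with the replacements allowed in Section 6 stated separately. The two changes belong together: on the assumed curves the corrected rule finishes within 12 patients in only 4% to 35% of trials, and within 18 in 89% to 96%. The plan should also say what happens in the remaining 4% to 11%.

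The cost is up to 6 more phase I patients than Sections 6 and 8.1 state, which Section 13 already allows. Phase II size and Tables 7 to 9 do not change.
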